## Inclusion and Exclusion Criteria

**Table 1. Criteria for study participants**

Inclusion	Exclusion
1) Living in the United States (contiguous states) 2) Aged 21 years or older	1) Under the age of 21 2) Received a positive test result more than 48 hours prior to contacting study staff or has a pending test for COVID19
3) Able to provide documentation of +PCR or +antigen test for COVID-19 within the past 48 hours 4) Self-reports that comfortable and willing to wear the wearable device and interact with a tablet-based interface daily	5) Able to provide a next of kin/designated person who can be contacted in the event of hospitalization for follow up. 3) Cannot confirm a PCR or antigen positive test for COVID-19 4) Is unable to read English

- |   |  |
|---|--|
| 
5) Is unwilling to wear the device 24 hours/day except for showering/bathing or interact with a tablet-based interface for daily questionnaire
 
6) Is unwilling or unable to provide baseline data required for entry into the study
 
7) Is unable to provide a next of kin/designated person who can be
 | 
contacted in the event of hospitalization for follow-up
 
8) Heavy tattooing on both upper arms
 
9) Known atrial fibrillation (permanent or paroxysmal)
 
10) Has taken/is taking part in a COVID-19 vaccine or treatment trial
 |
|---|--|
- 

## Pilot Phase

The pilot phase study with a goal of 50 participants will test the feasibility of recruitment, trial logistics, observed patient events, timeline to deterioration, and environmental test settings. The primary aim is to make any revisions to recruitment strategy and to the final number of “critical events” (e.g., hospitalization) required. The secondary aim is to produce descriptive statistics on pilot data and understand user issues that could affect study data. Descriptive statistics will include univariate analysis such as frequency, box plots, or histograms, and where appropriate, bivariate analysis on covariates using methods such as regression, Fisher’s exact tests, or chi-squared analyses.

## Algorithmic Approach – Bayesian Network

The proposed methodical approach will use a Bayesian network to predict risk/probability of the study outcomes. There are four levers to consider in model development that will be elaborated on separately: 1) variables in the model 2) characterization of variables 3) distribution of variables and 4) provided prior direction of effect. The latter two levers lend themselves more to Bayesian methods. Variables that will be collected in the study are outlined below, however each variable will need to be analyzed to determine statistical significance and interaction effects to determine if it belongs in the final model.

The characterization of variables refers to how they will be categorized, binned, or otherwise transformed, such as using multiple variables to make an aggregated score variable that acts as input to the risk model. For example, a continuous BMI variable may be taken and grouped it into clinical categories (e.g., normal, overweight, obese, etc.), then further combine the variable with a patient’s self-reported health to generate a “wellness score”. These variable transformations will be done iteratively in the training stage. The distribution of the variable is the percent in each category/bin. Traditional machine learning methods require that the distribution of a variable comes only from study data. However, in Bayesian methods if a value of interest is unknown or will not be able to be explicitly measured in the study, a *prior* can be provided to make inference; this is especially helpful in smaller sample sizes. For reference, a *prior*, of an uncertain quantity is the probability distribution that would express one’s beliefs about this quantity before some evidence is taken into account. An example of how prior probabilities from literature maybe incorporated in the study is to state the probabilities of false positives and false negative rates in positive COVID-19 nasal swab PCR testing. Direction of effect refers to the causal flow of Bayesian networks. These are prespecified by existing literature, clinical knowledge, and subject matter knowledge to

consider how one event precedes another. In this study design, such causal flow is able to explicitly state that infection precedes the onset of symptoms.

Finally, Bayesian networks are more transparent than other models, as they rely on traditional conditional probabilities, that is, how the likelihood of having a characteristic affects the likelihood of having another characteristic or the probability experiencing an event. Model transparency will likely help with clinical adoption and utility.

## **Stage 1**

### *Training Stage – Model Creation & Training Algorithm*

The overall aim of Stage 1 is to collect enough data to perform machine learning analytics on data from the Current Health device to create a Bayesian network algorithm that successfully predicts the risk/probability of no severe disease, hospitalization, ICU admission, and death following SARS-CoV-2/COVID-19 infection. The outcomes are *not* mutually exclusive categories, and can be hierarchical, i.e., when a patient first goes to hospital and then is admitted to the ICU. Conversely, a patient at risk could experience death without ever being hospitalized. This will be accounted for by calculating probabilities of each outcome and compare the conditional probabilities analyzing the risk of ICU admission, given that hospitalization has already occurred. One thousand participants will be recruited for the training stage.

A Bayesian network will first be developed using all 1000 participants in the training set. A Bayesian network illustrated (Appendix A, Fig1) has “nodes” which represent the variables and “arc” or “edge” which is the directional arrow drawn connecting the nodes. The probability of a “base model” is where no participant observations have been made, so each variable is the marginal (independent) probability. When information is input for each participant, i.e., in base model probability of sex is 50% male, 50% female, but once it is known a participant is male, the probability will be updated to 100% male. This in turn updates the risk probability of no severe disease, hospitalization, ICU, and death, now knowing the participant is male.

Once the Bayesian network model is constructed, to account for model variation, that is a model’s parameters change depending on the data the model is being given, nested crossvalidation will be performed to ensure model stability and reduce issues with overfitting. Sensitivity analysis will be conducted to determine variables that have most effect and are statistically significant to outcome variable also called a “target node”. If necessary, to further check data stability bootstrapping resampling will be explored.

Not all readings from the wearable are perfect, meaning some data from the wearable can be considered noise from factors such as wearing device in the wrong orientation (upside down) or large amounts of movement inhibiting reading. The study team will instruct participant on correct use of the wearable during onboarding then check the signal robustness to ensure noisy data is either transformed to be used or filtered out.

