#### Pilot

The pilot phase study with 50 participants will test the feasibility of recruitment, trial logistics, observed participant events, timeline to deterioration, and environmental test settings. The primary aim is to make any revisions to recruitment strategy and to the final number of “critical events” (e.g., hospitalization) required. The secondary aims are to produce descriptive statistics on pilot data, understand user issues that could affect study data, and begin formulating the structure of the Bayesian network. Descriptive statistics will include univariate analysis such as frequency, box plots, or histograms, and where appropriate, bivariate analysis on covariates using methods such as regression, Fisher’s exact tests, or chi-squared analyses.

#### Stage 1

The overall aim of Stage 1 is to collect enough data to perform machine learning analytics on data from the Current Health device to create a Bayesian network algorithm that successfully predicts the risk/probability of no severe disease, hospitalization, ICU admission, and death following SARS-CoV2/COVID-19 infection. The outcomes are *not* mutually exclusive categories, and can be hierarchical, i.e., when a participant first goes to hospital and then is admitted to the ICU. Conversely, a participant at risk could experience death without ever being hospitalized. This will be accounted for by calculating probabilities of each outcome and compare the conditional probabilities analyzing the risk of ICU admission, given that hospitalization has already occurred. One thousand participants will be recruited for the training stage.

Once the Bayesian network model is constructed, to account for model variation, that is a model's parameters change depending on the data the model is being given, cross-validation will be performed to ensure model stability and reduce issues with overfitting. Cross validation will only be conducted in the training data, as any cross validation with testing data has been shown in instances not to aid overfitting issues.

## Stage 2

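### Cross-validation is placed after the network has been built on all 1,000 training participants, so the Stage 1 AUC is likely to be optimistic unless selection and binning are repeated inside the folds

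*Combined protocol and SAP*

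**What the plan says.** **Selection and transformation.** The protocol's section on the algorithmic approach says that "each variable will need to be analyzed to determine statistical significance and interaction effects to determine if it belongs in the final model". It describes grouping variables and combining them into scores, and adds: "These variable transformations will be done iteratively in the training stage". It does not say on which data the significance analysis is run, at what threshold, or when relative to cross-validation. It does say that arc directions are set in advance from literature and clinical knowledge.

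**Order of steps.** Protocol, Stage 1: "A Bayesian network will first be developed using all 1000 participants in the training set". Then: "Once the Bayesian network model is constructed, to account for model variation", followed by "nested crossvalidation will be performed to ensure model stability and reduce issues with overfitting". The variation it means is the change in a model's parameters with the data supplied. A further significance step is listed after that: "Sensitivity analysis will be conducted to determine variables that have most effect and are statistically significant to outcome variable".

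**SAP.** Section 9.2, Stage 1, also puts cross-validation after construction, but without the word *nested*: "cross-validation will be performed to ensure model stability and reduce issues with overfitting". It adds: "Cross validation will only be conducted in the training data". SAP 6.3 mentions nested cross-validation as a proposed remedy for overfitting, but does not commit to it there.

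**Stage 2.** Both documents set aside a separate cohort of 1,000 for AUC, PPV and Brier scores, evaluated after each 100 participants.

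**The concern.** Cross-validation gives a fair estimate only of the steps that are repeated without the held-out fold. If the variables and their categories have already been chosen on all 1,000 participants, each held-out fold has helped to choose the model that it then tests. Re-estimating the probability tables in the remaining folds does not undo that. The procedure is then not nested cross-validation in substance, and its estimate tends to be too high.

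What is at stake is the team's view of the network at the end of training. Both documents justify the sample size partly by 100 events being enough to assess training performance, so the Stage 1 estimate has a role. If it is too high, a weaker network than believed goes to the one independent cohort, and the shortfall appears only there.

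**Working it through.** **1. The plan's own figures.** Neither document states a Stage 1 performance or optimism figure. The nearest figures are the sample-size calculations (protocol Appendix B, SAP 6.3).

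- Calculation 2: n = exp[(−0.508 + 0.259 ln 0.1 + 0.504 ln 30 − ln 0.05) / 0.544] = 755.9. The plan gives 756. Reproduced.
- Calculation 1, protocol form: (1.96/0.05)² × 0.1 × 0.9 = 138.3. The plan gives 139. Reproduced.

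Neither calculation addresses bias in cross-validation.

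**2. What is re-estimated in the folds, as written.**

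| Step | Where the documents place it | Repeated inside folds? |
|---|---|---|
| Variable selection by significance | Algorithmic approach; timing not given | Not stated |
| Binning and score construction | Training stage, iterative | Not stated |
| Network development | All 1,000, before cross-validation | Not stated |
| Parameter estimation | Named reason for cross-validating | Yes, by implication |

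No inner or outer loop is defined in either document.

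**3. Size of the effect, by simulation.** Inputs from the plan: 1,000 participants, 10% events (about 100), about 30 parameters, significance level 0.05. Assumptions: the general 0.05 level is used for screening; candidates are independent and cut at fixed tertiles; the model is naive Bayes, the simplest Bayesian network; there are 10 folds; candidates number 30, 100 or 300; and there are either no true predictors or 5 with a standardised shift of 0.3 or 0.4. New-data AUC comes from 10,000 fresh participants. Each scenario has 60 to 300 replicates.

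A = apparent AUC. B = cross-validated, screening done once on all 1,000. C = cross-validated, screening repeated in each fold. D = new data.

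| Candidates | True predictors | A | B | C | D | B − D | C − D |
|---|---|---|---|---|---|---|---|
| 30 | none | 0.572 | 0.551 | 0.498 | 0.501 | 0.050 | −0.003 |
| 30 | 5 at 0.3 | 0.693 | 0.650 | 0.617 | 0.622 | 0.028 | −0.005 |
| 30 | 5 at 0.4 | 0.739 | 0.700 | 0.682 | 0.687 | 0.013 | −0.005 |
| 100 | none | 0.650 | 0.599 | 0.498 | 0.498 | 0.101 | 0.000 |
| 100 | 5 at 0.3 | 0.732 | 0.672 | 0.598 | 0.605 | 0.067 | −0.007 |
| 300 | none | 0.759 | 0.672 | 0.497 | 0.500 | 0.172 | −0.003 |
| 300 | 5 at 0.3 | 0.799 | 0.715 | 0.569 | 0.574 | 0.141 | −0.005 |
| 300 | 5 at 0.4 | 0.819 | 0.746 | 0.626 | 0.629 | 0.117 | −0.003 |

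Screening outside the folds overstates AUC by 0.01 to 0.05 with 30 candidates, 0.07 to 0.10 with 100 and 0.12 to 0.17 with 300. Screening inside the folds stays within 0.01 of the truth throughout. Because the cut-points were fixed, these figures measure leakage through selection only. Outcome-driven binning is not included.

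**4. How many candidates?** SAP 8.5 and 8.6 list 23 intake items, 19 daily-survey items and 6 wearable signals, excluding free text: 23 + 19 + 6 = 48. That is before dummy categories, daily repeats, combined scores or rolling summaries. The number actually screened is not given.

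**The case against.** **The protocol names nested cross-validation.** Done properly, it repeats selection inside the folds and removes the bias, as column C shows. This stands as far as it goes: the defect is a procedure that is not specified, with an order of steps that contradicts the label, rather than a proven wrong method. But SAP 9.2 drops the word, and the stated reason for cross-validating concerns parameters only.

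**Screening on all 1,000 before cross-validation is not stated.** This is correct. It is the natural reading of the algorithmic-approach and Stage 1 sections together, but it is an inference, and the significance step within the Stage 1 sequence comes after cross-validation.

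**Some structure is not learned from these data.** Arc directions are prespecified, the pilot informs the design of the network, and the one binning example uses clinical BMI groups. So leakage would come mainly from which variables are kept and from any data-driven cut-points.

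**A reader might infer that this cross-validation cannot detect overfitting at all.** The results do not support that. With 30 candidates and 5 true at 0.3, it removes (0.693 − 0.650)/(0.693 − 0.622) = 0.043/0.071, about 61% of the apparent optimism. With 300 candidates it removes (0.799 − 0.715)/(0.799 − 0.574) = 0.084/0.225, about 37%.

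**A reader might also infer that the Stage 1 AUC decides whether the model is frozen, or that the final results will be inflated.** Neither document makes the Stage 1 AUC such a criterion, and the performance metrics come from a separate cohort. The acceptance rule of AUC above 0.75 (SAP 5.2 and 6.4) does not name its data set, however, and no passage states a model lock. The protocol's Stage 2 subtitle allows for further model creation, and the cohort is evaluated 1,000/100 = 10 times.

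**Relevant text may not be visible.** SAP Section 12 refers to added detail on structural and parameter learning and to a section 9.5. The contents list ends Section 9 at 9.2.

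**Conclusion.** The point holds as a conditional one. If the stated order is followed, and selection and binning use all 1,000 participants before the folds are formed, the Stage 1 AUC is likely to be optimistic: by about 0.01 to 0.05 at the plan's 30 parameters, and by 0.07 to 0.17 with 100 to 300 candidates. The 48 listed items fall between the first two settings. The larger figures need many features derived from the wearable signals, a number that the documents leave open.

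The size rests on independent candidates, a 0.05 screen and naive Bayes. The upper end at each candidate count comes from scenarios with no true predictor, which is unlikely here because the baseline variables were chosen from known risk factors. The direction of the bias does not depend on these choices; its size does.

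The documents do not support saying that Stage 1 performance will certainly be overstated, or that the final Stage 2 metrics are biased. A model locked before Stage 2 gives held-out metrics free of this problem. The point is worth correcting before training starts, but it does not undermine the validation design.

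**What to change.** In protocol Stage 1 and SAP 9.2:

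- State that data-driven variable selection, binning, score construction and any structure learning are repeated within every outer training fold, with tuning in an inner loop. Steps set in advance from literature or clinical knowledge need not be repeated; list which these are.
- Restore the word *nested* in SAP 9.2 so that the two documents agree.
- Record the nested estimate first, then refit once on all 1,000.
- Lock that refitted model before any Stage 2 data are evaluated.

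Replacing the significance screen by another selection method is optional and not part of this fix, since the screen was nearly unbiased once it was inside the folds (column C against column D).

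The cost is SAP and protocol wording, more computing time, and a somewhat lower Stage 1 AUC. No extra participants or data are needed.

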## **Stage 2**

### *Testing Stage – Expansion for Model Creation or Validation*

To assess the algorithm performance, algorithm testing on a total of 1,000 participants will be conducted. This cohort of 1,000 testing participants will be held entirely separate from the

training participants to minimize data snooping bias in the study. In machine learning, it is typical to obtain initial testing cohort results to determine if the model created from the training data is performing well. After the first 100 participants in the testing cohort are monitored for 30 days, the algorithm will be tested for understanding initial performance. As more participants are recruited into the study, follow-up algorithm testing will occur for each 100 participants that are added to the testing cohort.

Although the outcome of the participants in the validation set is known, the outcomes will be initially ignored, as if researchers did not know participant outcome. This simulates what researchers know about a participant, preceding the participant's outcome. The testing participants' collected variables (demographic, medical history, continuous data from wearable, and symptom data) will be run through the developed Bayes network algorithm and comparison models. The algorithm will return probabilities of the study outcomes. The algorithm's probabilities will then be compared with the true outcome of the participant recorded by the study team.

The differences between the algorithm prediction and participant's true outcome will be used to calculate performance metrics such as positive predictive value (PPV), area under the curve/receiver operating characteristic (AUC/ROC), and Brier scores. The final part of algorithm validation will be calibration analysis, sensitivity analysis, and determining any subpopulations that may have had poor predictive performance.

The benchmarks of model performance will be as follows: area under curve between 0.50 and 0.55 is poor, 0.55 to 0.65 is moderate, 0.65 to 0.75 is acceptable, and >0.75 is excellent. Brier scores will be used to verify the accuracy of the event prediction during calibration, where a perfect score is 0 and imperfect score is 1. Different specificity and sensitivity levels will need to be considered when creating a feature that automatically triggers notification of study staff that a participant is likely (probability of hospitalization >50%) to reduce alarm and alarm fatigue. In addition, the duration of time a patient spends in a high-risk state needs to be considered. For example, if a participant's oxygen saturation levels (SpO2) levels decrease for a brief period, then regain to normal levels, we will evaluate this to determine if it is an indicative of patient deterioration or not.

We hypothesize that our model will achieve an accuracy of 75% or higher.

**Table 2. Variables collected for analysis**

Table 2. Variables collected for analysis	
Continuously acquired variables	Categorical variables (continued)
1. Respiration rate	13. Age
2. Pulse rate	14. Sex
3. Oxygen saturation	15. Occupation
4. Skin temperature	16. Household make-up (living alone or with people)
5. Step count	17. Other household members with COVID19
6. Activity levels	18. Other household members enrolled in this study
Categorical variables	19. Menopausal state and time since last menstrual cycle / Pregnancy status
7. Symptoms	20. Race/Ethnicity
8. Days when reporting for employment	21. Zip code
9. Outcomes of any SARS-CoV-2/COVID-19 testing	22. BMI (height & weight)
10. Admission to hospital, ICU, death	23. Comorbidities
	24. Acute and Chronic Medication

## Recruitment Strategies

The primary recruitment tactics will involve digital marketing through social media (Facebook Advertising), and Google Advertising. We will use CDC data to target areas experiencing outbreaks of SARS-CoV-2/COVID-19. Additional recruitment tactics include email content and circulation of physical materials such as flyers, posters, or bulletin boards and direct mailers. All marketing material will direct to the website, including study team contact information, for initial screening. Throughout the enrollment process, Current Health will communicate updates on the clinical trial and/or enrolment process via phone calls, text messages, or emails. All materials will be developed by Current Health, reviewed by BARDA funders, and approved by the Advarra Institutional Review Board before becoming patientfacing. No communications via email or text message will contain protected health information.

We plan to create a website to serve as the primary communication method with participants prior to enrollment in the clinical trial. This website (<https://community.currenthealth.com>) sits as a subdomain on the Current Health corporate website, which is secure and HIPAA compliant. We have included the website wording, and sample screenshots as appendices.

On the website, we articulate:

- The goals of the clinical trials
- Qualification criteria for participants
- What is expected of participants as part of the clinical trial
- What compensation the participant can expect to receive
- Support contact information for participants enrolled in the clinical trial

- Information regarding Current Health

Once participants have progressed through the website, their details will be passed to a study team member. The study team member will contact the participant via email or text message and send a copy of the Informed Consent Form. The study team member and participant will arrange a mutually convenient time to speak via telephone or Zoom. Together, they will review the Informed Consent Form and engage with the process of consent. Once consent has been obtained via secure electronic means, the participant will be shipped a Current Health device by a logistics partner (Seko).

